3.1 General Design

This is a Phase II double-blind randomized controlled clinical trial. The hypotheses in the proposed study will be tested with a 2-group design to assess the efficacy of varenicline as compared to placebo. We will follow NIAAA's COMBINE Medical Management (MM) manual in weekly dispensing medications, safety checks and medication adherence. The psychosocial treatment will be Cognitive Behavioral Coping Skills Therapy (CBT). Subjects will be 200 men and women with current DSM-IV diagnoses of cocaine dependence that will be randomized to receive either varenicline or placebo (100 subjects per group). All subjects will

receive weekly sessions of CBT. The study length for each subject is comprised of 1-4 weeks of screening (referred to as “week 1”) and a 12-week double-blind, placebo-controlled trial with CBT (medication phase). *At the end of the study subjects will be referred to continuing care programs in the community.*

3.2 Primary Study Endpoints

Primary Hypothesis:

- Subjects receiving varenicline will have higher rates of cocaine abstinence than will those receiving placebo, as determined by urine assay for benzoylecgonine (BE), the primary metabolite of cocaine.

3.3 Secondary Study Endpoints

Secondary Hypotheses:

- We further hypothesize that within the varenicline group, medication compliant participants ($\geq 80\%$ of pills taken) will have higher rates of cocaine abstinence than those who are non-compliant ($< 80\%$ of pills taken).
- We expect that the varenicline group will report less craving for cocaine than will the placebo group, as measured by lower scores on the Cocaine Craving Questionnaire (Tiffany et al., 1993) and the Minnesota Cocaine Craving Scale (Halikas et al., 1991) during the medication treatment phase.
- We expect that the varenicline group will show greater decreases in cigarette smoking than will the placebo group, as evidenced by CO and cotinine levels.

• Primary Safety Endpoints

A nurse or physician will assess for adverse events weekly. Adverse events will be monitored by research staff at all other visits, and the psychiatrist or nurse will be available at other visits to assess the subject if needed. At the conclusion of medications, an end of study physical will be completed and the baseline laboratory tests, including EKG, will be repeated. If the subject is discontinued in treatment due to a serious adverse event, the subject will be followed clinically by medical staff until the adverse experience resolves itself and becomes stable.

4 Subject Selection and Withdrawal

4.1 Inclusion Criteria

1. Males and females, 18 to 65 years old.

2. Meets DSM-IV criteria for Cocaine Dependence, as determined by the Structured Clinical Interview for DSM-IV (SCID).
3. Live within a commutable distance of the Treatment Research Center (TRC) at the Penn/VA Center for Studies of Addiction, University of Pennsylvania. **We define this to be a distance within the service area of Septa, within an hour drive, or a distance that both the participant and Principal Investigator (PI) find acceptable.**
4. Understands and signs the informed consent.

4.2 Exclusion Criteria:

1. Current DSM-IV diagnosis of any psychoactive substance dependence other than cocaine, alcohol or nicotine dependence, as determined by the SCID.
2. Subject is, in the investigator's opinion, at risk of requiring medical detoxification for alcohol dependence during the study.
3. Concomitant treatment with psychotropic medications.
4. Current gambling problems. **This will be assessed by the participant's self-report.**
5. Participants mandated to treatment based upon a legal decision or as a condition of employment who will use participation in this study to fulfill their court mandated treatment requirement.

This will be assessed by the participant's self-report.

6. Current severe psychiatric symptoms, e.g., psychosis, dementia, suicidal or homicidal ideation, mania or depression requiring antidepressant therapy in the opinion of the **Principal Investigator (PI)**.
7. Use of any investigational medication within the past 30 days.
8. Subject **has serious heart, lung, kidney, immune system, GI tract (ulcerative colitis, regional enteritis, or gastrointestinal bleeding) disease.**
9. Current use of naltrexone, disulfiram, modafinil, stimulants, haloperidol, benzodiazepines or anticonvulsants. **Anticonvulsants (e.g., gabapentin) prescribed for pain is not exclusionary.**
10. Known hypersensitivity to varenicline.
11. Participants with **known** AIDS or other serious illnesses that may require hospitalization during the study.
12. Female subjects who are pregnant or lactating, or female subjects of child-bearing potential who are not using acceptable methods of birth control. Acceptable methods of birth control include:
 - a. barrier (diaphragm or condom) with spermicide
 - b. intrauterine progesterone contraceptive system
 - c. levonorgestrel implant
 - d. medroxyprogesterone acetate contraceptive injection
 - e. oral contraceptives
 - f. tubal ligation.
13. Participants with impaired renal function as indicated by corrected creatinine clearance below 60 ml/min as determined by the modified Cockcroft equation.
14. Clinical laboratory tests (CBC, blood chemistries, urinalysis) outside normal limits that are clinically unacceptable to the Medical Director. EKG-1st degree heart block, sinus

tachycardia, left axis deviation, and nonspecific ST or T wave changes are allowed; liver function tests [LFTs] <5 x ULN are acceptable).

4.3 Subject Recruitment and Screening

The proposed project will be conducted at the University of Pennsylvania's Treatment Research Center (TRC). The TRC is a community-based (non-veteran) outpatient addiction treatment-research program that is part of the University of Pennsylvania Center for the Study of Addictions ([name], Director). The TRC offers outpatient addiction treatment for individuals from the greater Philadelphia area who are seeking treatment for their addiction and who qualify for one of our grant-sponsored treatment studies on alcohol, cocaine, dual cocaine-alcohol, marijuana, heroin or nicotine dependence. Subject recruitment is ongoing and accomplished through community, professional, and self-referrals from the greater metropolitan Philadelphia area. Most of the TRC callers seeking treatment who are approved for intake (via phone pre-screen) and give written consent (93%) are subsequently randomized (85%) into a treatment-research study. All subjects enrolled at the TRC receive medical monitoring and high-quality treatment—at no cost. Female-focused recruitment strategies, including direct appeals to female-medical specialties such as OB-GYN offices, has increased our ability to recruit female cocaine and alcohol dependent subjects.

Prior to participating in treatment-research studies at the TRC, all subjects undergo a medical and psychosocial intake to determine health and potential eligibility for treatment in one of the TRC's research programs. Routine measures obtained on the first day the subject arrives at the TRC are a psychosocial history, medical history, and the Beck Depression Inventory (BDI).

Before study-specific eligibility criteria are assessed, subjects are asked for their consent. At the consent session, all assessments, lab procedures and information on study medications are fully explained. Subjects are given information about confidentiality, study payments and under what circumstances they may be prematurely discontinued from treatment. Subjects are told that a blood alcohol concentration (BAC) reading will be required at each TRC visit, and that the reading must be below 0.02, otherwise the visit will be rescheduled. If their BAC reading is 0.08 or higher, they will be detained until arrangements are made for them to be escorted home or the reading decreases to an acceptable level (e.g., 0.02). At the end of the session, subjects take a consent “quiz” that can be re-taken until all of the questions are answered correctly. Subjects then give written consent and are given phone numbers of key project staff and a 24-hour emergency number. After signing informed consent, subjects continue with screening assessments to determine if they meet eligibility criteria.

Subsequent screening procedures include blood chemistry, CBC, urinalysis, psychiatric interview, assessment of baseline drug and alcohol use using the Timeline Follow Back, Addiction Severity Index.

4.3.1 Genetics of Addiction

The TRC has a Genetics Research Bank to collect and store samples from individuals participating in research studies at the University of Pennsylvania Treatment Research Center (TRC). Individuals providing blood samples will have screened and/or participated in various research studies focused on an addictive disorder. These samples will be used to study various candidate genes and/or whole genomes and their relationship to clinical and demographic data collected as part of the other research studies that the individual has participated. The Genetics of

Addiction study stopped recruitment on 01/07/2015. Persons participating in the intake process for research studies at the TRC are no longer eligible to sign a separate consent for the Genetics of Addiction study. Persons reporting for intake have usually undergone a telephone or in-person screening to see if they are eligible for ongoing studies at the TRC. Participants who signed consent for the Genetics of Addiction study during the recruitment phase had two vials of blood drawn to analyze their genotype, as outlined in the Genetics of Addiction protocol.

This study (Varenicline for Cocaine) does not have any genetic hypotheses. As such, the information obtained from the genetics blood bank will not be shared with the Principal Investigator of this study by [name], the Principal Investigator of the Genetics of Addiction study. As such, the below language (taken from study consent) addresses the non-linkage between the two studies:

"In addition to your participation in this trial, you may have also consented to a separate study of the Genetics of Addiction. If you consented to the Genetics of Addiction study, those results are separate from this trial and will not be combined with the results from this trial. If you have any concerns about your participation in the Genetics of Addiction study, please discuss with the research staff."

4.4 Early Withdrawal of Subjects

4.4.1 When and How to Withdraw Subjects

Clinical Trial Discontinuation Criteria: All randomized subjects are included in the intent-to-treat analysis. All subjects who prematurely discontinue treatment will be scheduled for a final evaluation, the end-of-trial visit. Subjects will also be given appropriate treatment referrals. Subjects are not dropped from all study activity unless they request they not be contacted, or the subject cannot be located for assessment. Subjects will be informed at the consent session that medications may be discontinued due to: 1) Intolerable side effects; or 2) Extreme lab values with a repeat test. In these two cases, the subjects may continue with the CBT part of the treatment, as well as receive medical attention. Subjects will be informed at the consent session that he or she may be discontinued from all treatment due to: 1) Development or exacerbation of significant psychiatric or medical symptoms that necessitate inpatient admission or a more aggressive therapeutic intervention than provided by the protocol; these subjects would not be invited back to take study medication but will be followed for data collection and may remain eligible for psychosocial treatment; 2) A return to significant cocaine use or emergence of another substance abuse problem which necessitates inpatient admission or a more aggressive treatment than provided by the protocol; subjects who are admitted for inpatient stabilization for cocaine use may return for data collection and psychosocial treatment after discharge to complete the 12 week trial, but study medication will not be restarted if they miss more than two weeks of study medication; 3) Incarceration > 1 week; subjects may return for data collection and psychosocial treatment after discharge to complete the 12 week trial but study medication will not be restarted if they miss more than two weeks of study medication 4) subject's behavior compromises subject's safety. The reason the subjects are discontinued from medication and/or the clinical trial and any referrals made are documented in a Note to File found in the subject's source document binder or medical chart. Study medications will not be restarted in subjects missing more than two weeks of study medications because this would necessitate restarting the dose titration schedule and may result in

a significant confound in the analysis of medication response. Varenicline can be abruptly stopped in patients without significant adverse effects.

4.4.2 Data Collection and Follow-up for Withdrawn Subjects

Standard procedures developed here at TRC are used to help locate missing subjects. These include the identification and verification of home and work phone numbers, emergency contacts and collateral contacts. Subjects who have missed an appointment are re-contacted initially by phone, then by letter and finally by registered mail. Emergency and other collateral contacts are used when subjects themselves cannot be contacted. Contacts are attempted daily for a minimum of one week then less frequently by mail. Subjects are not considered lost to follow up until the entire study is completed and the database is ready to be closed.

5 Study Drug

5.1 Description

Maximum plasma concentrations of varenicline occur typically within 3-4 hours after oral administration. Following administration of multiple oral doses of varenicline, steady-state conditions were reached within 4 days. Over the recommended dosing range, varenicline exhibits linear pharmacokinetics after single or repeated doses. In a mass balance study, absorption of varenicline was virtually complete after oral administration and systemic availability was high. Oral bioavailability of varenicline is unaffected by food or time-of-day dosing. Plasma protein binding of varenicline is low ($\leq 20\%$) and independent of both age and renal function.

Metabolism/Elimination

The elimination half-life of varenicline is approximately 24 hours. Varenicline undergoes minimal metabolism with 92% excreted unchanged in the urine. Renal elimination of varenicline is primarily through glomerular filtration along with active tubular secretion possibly via the organic cation transporter, OCT2.

Study medication will be prepared by the Research Pharmacist at the Hospital of the University of Pennsylvania by over-encapsulating varenicline 0.5 and 1.0 mg capsules.

5.2 Treatment Regimen

Study medication will be initiated in Week 2. The research physician or nurse will explain the dosing regimen and subjects will be randomized to receive either varenicline or placebo. The statistician will randomize subjects to either varenicline or placebo using a computer-generated program of urn randomization, based on specified criteria that are described below.

The dose of varenicline will begin at 0.5 mg daily, and will be titrated up to the target daily dose of 2.0 mg/day at the start of the second week of medication (see Table 1). If adverse events occur, the physician or nurse may keep the dose the same or reduce to fewer pills. If the side effects subside, subjects can be re-challenged or kept at a lower number of pills. During the last week of the medication phase of the trial, varenicline will be reduced to 1.0 mg daily.

Pharmacotherapy will be completed by the end of the 13th week. If tolerated, subjects will be taking the maximum daily dosage (2.0 mg of varenicline or identical appearing capsules) for 10 weeks (Weeks 3-12).

Table 1. Dosing Schedule (taken from package insert)

| Wk. | Daily Dose |
|--------------|---------------------------|
| 2 (days 1-3) | 0.5 mg |
| 2 (days 4-7) | 0.5 mg BID (1.0 mg daily) |
| 3 | 1.0 mg BID (2.0 mg daily) |
| 4 | 1.0 mg BID (2.0 mg daily) |
| 5 | 1.0 mg BID (2.0 mg daily) |
| 6 | 1.0 mg BID (2.0 mg daily) |
| 7 | 1.0 mg BID (2.0 mg daily) |
| 8 | 1.0 mg BID (2.0 mg daily) |
| 9 | 1.0 mg BID (2.0 mg daily) |
| 10 | 1.0 mg BID (2.0 mg daily) |
| 11 | 1.0 mg BID (2.0 mg daily) |
| 12 | 1.0 mg BID (2.0 mg daily) |
| 13 | 0.5 mg BID (1.0 mg daily) |

There have been no severe interactions noted between varenicline and any other drugs. Nonetheless, in the proposed study, weekly monitoring by a nurse or physician provides a safety net. We will be monitoring adverse events via self-reports, BAC readings, and liver enzymes collected routinely during the trials. Side effects can be treated by lowering the dose of study medications or discontinuing the study medications when necessary. The subject will be discontinued from medications if he or she has experienced a medication associated serious adverse event (SAE), cannot tolerate minimum dosages of study medication, or becomes pregnant. Any subject who is discontinued from the study medications can still complete the CBT portion of the treatment. If the subject reports an SAE, the subject will be followed until the event is resolved. Federal, sponsor, and institutional guidelines are followed for reporting SAEs.

Clinical Deterioration and/or Suicide Risk Management: All of the investigators have had experience managing and referring subjects under these conditions. We follow the TRC's standing emergency policy when managing clinical deterioration related to addiction or psychiatric symptomatology for all of our subjects. At the weekly visit, subjects are evaluated for the presence or persistence of any symptoms indicative of clinical deterioration due to a rapidly increasing problem with cocaine use, drinking, and/or psychiatric symptoms, including suicidality. Between visits, subjects are instructed to contact their treating physician or an authorized research staff member in the event that disturbing symptoms become evident. In all cases, these subjects are immediately evaluated, and if deemed appropriate, are referred to clinical treatment. If possible, they will be maintained in the trial as long as all it is deemed safe to do so. Also, any additional treatment is recorded for data analysis purposes. At any time, subjects who are severely suicidal or at high risk of medical or physical harm will be immediately discontinued from the trial. All subjects who are discontinued from the trial are still encouraged to attend the end of treatment visit.

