All patients being treated with CHANTIX should be observed for neuropsychiatric symptoms including changes in behavior, hostility, agitation, depressed mood, and suicide-related events, including ideation, behavior, and attempted suicide. These symptoms, as well as worsening of pre-existing psychiatric illness and completed suicide, have been reported in some patients attempting to quit smoking while taking CHANTIX in the postmarketing experience. When symptoms were reported, most were during CHANTIX treatment, but some were following discontinuation of CHANTIX therapy.

These events have occurred in patients with and without pre-existing psychiatric disease. Patients with serious psychiatric illness such as schizophrenia, bipolar disorder, and major depressive disorder did not participate in the premarketing studies of CHANTIX, and the safety and efficacy of CHANTIX in such patients has not been established.

Advise patients and caregivers that the patient should stop taking CHANTIX and contact a healthcare provider immediately if agitation, hostility, depressed mood, or changes in behavior or thinking that are not typical for the patient are observed, or if the patient develops suicidal ideation or suicidal behavior. In many postmarketing cases, resolution of symptoms after discontinuation of CHANTIX was reported, although in some cases the symptoms persisted; therefore, ongoing monitoring and supportive care should be provided until symptoms resolve. The risks of CHANTIX should be weighed against the benefits of its use. CHANTIX has been demonstrated to increase the likelihood of abstinence from smoking for as long as one year compared to treatment with placebo. The health benefits of quitting smoking are immediate and substantial.

Drug Interactions

Based on varenicline characteristics and clinical experience to date, CHANTIX has no clinically meaningful pharmacokinetic drug interactions.

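### For new suicidal ideation below the removal threshold, the visible rules in 5.2 and 4.4.1 require evaluation but set no default drug hold, and so are narrower than the boxed warning the protocol reproduces

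*Combined protocol and SAP*

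**What the plan says.** **Label text.** Section 1.3 reproduces the boxed warning. It advises patients to stop the drug and contact a provider at once for several symptoms, "or if the patient develops suicidal ideation or suicidal behavior". No severity threshold is attached.

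**Mandatory drug stop (5.2).** "The subject will be discontinued from medications if he or she has experienced a medication associated serious adverse event (SAE), cannot tolerate minimum dosages"; pregnancy is the remaining ground.

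**Mandatory removal (5.2, suicide risk management).** "subjects who are severely suicidal or at high risk of medical or physical harm will be immediately discontinued from the trial".

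**Below that level (5.2).** "In all cases, these subjects are immediately evaluated, and if deemed appropriate, are referred to clinical treatment". Subjects are then kept in the trial where possible while that is judged safe. For adverse events generally, "If adverse events occur, the physician or nurse may keep the dose the same or reduce to fewer pills". Section 5.2 also allows drug to be discontinued when necessary, and section 1.3 lists temporary cessation among the options for managing an adverse event.

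**Instruction to subjects (5.2).** "Between visits, subjects are instructed to contact their treating physician or an authorized research staff member in the event that disturbing symptoms become evident".

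**Withdrawal criteria (4.4.1).** "Subjects will be informed at the consent session that medications may be discontinued due to: 1) Intolerable side effects; or 2) Extreme lab values" confirmed on repeat testing. Possible grounds for ending all treatment include "Development or exacerbation of significant psychiatric or medical symptoms that necessitate inpatient admission or a more aggressive therapeutic intervention than provided by the protocol"; once that ground is applied, study drug is not resumed. Behavior that compromises the subject's safety is another ground.

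**The concern.** The protocol states one threshold in its risk section and a higher one in its operating sections. A subject who reports new ideation that is not judged severe must be evaluated, but may then continue on the same blinded dose without anyone having to record why. A drug stop becomes mandatory only if blinded staff judge the event both serious and medication-associated, or if another listed ground is met. The label advice depends on neither judgment. A subject at home who has not yet reached staff has no visible instruction to leave the capsules alone.

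What is at stake is the safety of a small number of subjects on a drug carrying this warning.

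**Working it through.** The plan gives no figure to reproduce. The check is a comparison of texts, followed by the cost of a hold.

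**Texts side by side, for new ideation that is not severe**

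| Question | Boxed warning (1.3) | Operating text |
|---|---|---|
| Does ideation alone trigger a drug stop? | Yes, at any severity | Not named in the 5.2 stop list or the 4.4.1 medication list |
| What is mandatory? | Stop and contact a provider | Immediate evaluation (5.2) |
| What may staff do? | Not addressed | Keep, reduce, hold or stop the dose (1.3, 5.2) |
| What is the subject told? | Stop and call | Call (5.2) |

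Staff therefore have the power to hold drug. What is absent is a default. The table of contents lists a section 8.5 on stopping rules, but 8.5 in the body is Medical Monitoring and contains none.

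**Cost of a hold.** Inputs: Table 1 in 5.2 (dosing schedule), 4.4.1 (drug is not restarted after more than two weeks missed) and the 80% compliance cut-off in 3.3 and 7.2. Doses are counted, not milligrams.

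- Week 2, days 1–3: 3 × 1 = 3.
- Week 2, days 4–7: 4 × 2 = 8.
- Weeks 3–12: 70 × 2 = 140.
- Week 13: 7 × 2 = 14.
- Total: 3 + 8 + 140 + 14 = 165.

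One-day hold: at most 2/165 = 1.2%.

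Longest restartable hold, 14 days: at most 28/165 = 17.0%, leaving 165 − 28 = 137 doses.

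- Perfect adherence otherwise: 137/165 = 83.0%, above the cut-off.
- Doses needed for 80%: 0.80 × 165 = 132, so 132/137 = 96.4% of the remaining doses must be taken.
- At 95% adherence otherwise: 0.95 × 137 = 130.15, and 130.15/165 = 78.9%, below the cut-off.

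A long hold can therefore turn a good adherer into a non-complier under Hypothesis 2.

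**Unreported interval.** A subject who does not call between a Friday and a Monday visit could take about 3 × 2 = 6 further doses.

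**Frequency.** Section 1.3 classes suicidal ideation as rare. It is not among the possibly related events reported by at least 5% of the 77 pilot subjects. No rate for this population is given, so no number of affected subjects is calculated.

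**The case against.** The strongest case against is that the protection already exists. Suicidality is assessed weekly, adverse events are sought at every contact, visits are three times a week, and a 24-hour number is provided. Current suicidal ideation is an entry exclusion. Evaluation is immediate, and staff may hold or stop drug. All of this stands. A reader might infer that the protocol leaves clinicians unable to hold drug; the documents say the opposite.

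A reader might also infer that subjects are never told to stop. The documents do not support that either. Section 1.3 says consent covers safeguards and emergency procedures, and 5.2 adopts the centre's standing emergency policy. The consent form, that policy, the Medical Management manual and the attached prescribing information are not in the review copy and may carry the instruction.

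A third objection is that a hold until evaluation does not prevent a restart and, with a half-life of about 24 hours (5.1), changes exposure little if it lasts hours. This is correct. The hold changes the default and requires a documented reason; it does not guarantee that drug stays off.

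The permission to keep the dose the same can be read as being about titration, since it follows the titration sentence. Its wording covers adverse events generally, however, and the suicide-risk text says nothing about study drug.

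Finally, the warning also names agitation, hostility, depressed mood and atypical behavior, so limiting a hold to suicidality is a judgment. Section 6 lists depressed mood among common effects of stopping cocaine, and section 1.3 lists depression as frequent, which argues against an automatic hold for mood. That reasoning does not cover agitation or hostility. The choice there remains the sponsor's.

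**Conclusion.** The point holds as a mismatch within the visible protocol. For new ideation below the removal and stop triggers, 5.2 and 4.4.1 do not carry through the label's advice to stop, and they allow dosing to continue unchanged after evaluation. This is not evidence that clinicians lack authority or that subjects are uninformed.

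The number of subjects affected is probably small but cannot be estimated from the documents. The primary result is unaffected: randomized subjects stay in the intent-to-treat analysis, and a hold would be applied blind in both arms. The dose figures rest on the Table 1 schedule; the 83.0% figure also assumes perfect adherence outside the hold. Priority is low to moderate, justified by the seriousness of the possible harm and the low cost of the change.

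**What to change.** First check the consent form, Medical Management manual, prescribing information and emergency policy, and match any stop instruction already there. Then:

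1. In 5.2, after the pregnancy ground for stopping drug, add: *For any new suicidal ideation or behavior, whatever its judged cause, study drug will be held until a study physician (in person or the on-call doctor) has evaluated the subject and documented the reason for restarting or stopping it. Unless the subject meets the removal rule below for severe suicidality or high risk of harm, which takes precedence, or a 4.4.1 ground for stopping all treatment, CBT, visits and data collection continue.*
2. To the between-visits sentence in 5.2 add: *and, for suicidal thoughts or behavior, to take no more capsules until evaluated.*
3. In 4.4.1, cross-refer to the 5.2 hold. Do not add ideation to the list of reasons for which medication may be discontinued: that list is permissive and would conflict with a mandatory hold.
4. In 7.2, flag protocol-directed hold days in the Hypothesis 2 compliance variable, so that they are not counted as the subject's own non-compliance.

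Leave the two-week restart limit and the removal rule unchanged.

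The cost is a short amendment, a line in the consent form if it is not already there, some on-call physician time, and the lost doses shown above. No scheduled visit or instrument is added. No taper is needed, since 4.4.1 states that varenicline can be stopped abruptly without significant adverse effects.
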